## What is already known on this subject? AND What does this study add?

Apart from surgical procedures, there are numerous hormonal and non-hormonal drugs for management of leiomyoma. One of the non-hormonal drugs is *N*-acetyl cysteine (NAC), but its use for this indication is poorly understood (*Aghaamoo et al., 2021*)

This randomized controlled comparative clinical trial will assess the impact of Dienogest versus *N*-Acetyl Cysteine in management of women with uterine leiomyoma.

## 1. INTRODUCTION/ REVIEW

Leiomyoma is a relatively common benign tumor. It is the most common cause of abnormal uterine bleeding and pelvic pain (*Ali et al., 2018*).

Leiomyoma originates from the smooth muscle of the uterus and its incidence is 4.5%–68.6%. In black women, the prevalence is doubled and they have higher numbers of leiomyoma and more severe symptoms than white women (*Vercellini and Frattarulo, 2017*)

Leiomyoma is symptomatic in patients and there are numerous clinical presentations, for instance, pressure on adjacent organs, infertility, abnormal uterine bleeding, and obstetric complications (*Stewart et al., 2017*)

Leiomyoma is considered the most common cause of gynecologic surgery worldwide (*Yuan et al., 2021*)

Recent research has succeeded in stemming the leiomyoma and found a multi-factorial inheritance pattern, but leiomyoma is still a matter of debate by experts and poses tremendous challenges (*Ayakannu et al., 2019*)

More than 100 gene abnormalities are identified in leiomyoma, in the genes for estrogen receptors, progesterone receptors, growth factors, prolactin receptors, extracellular matrix, and collagens (*Sogoyan et al., 2020*)

Apart from surgical procedures, there are numerous hormonal drugs for leiomyoma. Dienogest is a selective progestin that combines the pharmacologic properties of 19-norprogestins and progesterone derivatives, offering potent progestogenic effects without androgenic, mineral corticoid, or glucocorticoid activity (**Caruso et al., 2019**)

Previous trials demonstrated that dienogest provides effective reductions in endometriosis-associated pelvic pain and laparoscopic measures of pathology (**Taylor et al., 2021**)

Recently, the new progesterone 2 mg daily demonstrated equivalent efficacy to GnRHa (e.g., buserelin acetate and leuprolide acetate) for relieving the pain of endometriosis in two 24 week randomized studies (**Marquardt et al., 2019**)

Because uterine myomas and endometriosis have many common features, these successful trials on endometriosis support that the use of dienogest inhibits myoma growth. While evaluating superiority of dienogest in women with endometriosis, significant shrinkage of myoma nodes was found coexisting with endometriosis over several months during an administration of dienogest (**Pratts et al., 2015**)

One of the non-hormonal drugs suggested for management of leiomyoma is *N*-acetyl cysteine (NAC), but its use for this indication is poorly understood. NAC is a medication that was used to treat paracetamol overdose, and in chronic obstructive pulmonary disease (**Aghaamoo et al., 2021**)

It can be prescribed intravenously, orally, or inhaled as a mist. However, in leiomyoma, NAC is based on a simple premise. It is an anti-oxidative drug that inhibits free oxidative radicals and consequently neutralizes the proliferation of the tumor cells (**Izadi et al., 2014**)

Adverse effects have been reported for NAC, including stomatitis, nausea, vomiting, fever, rhinorrhea, drowsiness, fatigue, chest tightness, and bronchoconstriction. NAC-induced bronchospasm occurs clinically rarely and unpredictably, even in patients with asthma bronchitis or bronchitis that complicates bronchial asthma (**Farris et al., 2019**)

Acquired hypersensitivity to NAC has been reported, also rarely. Sensitization reports in patients with patch testing have not been confirmed.

Sensitivity has been confirmed by several inhalation therapists who have reported a history of skin eruption after repeated and prolonged contact with NAC (*Timuroğlu et al., 2018*)

There is a consensus of opinion concerning the anti-oxidative effect of NAC, but it is difficult to assess its effectiveness in leiomyoma. Not only would using NAC avoid some of the adverse effects of hormonal drugs, but NAC is also cheaper than the hormonal alternatives. This spurs efforts to develop non-hormonal therapies in leiomyoma (*Aghaamoo et al., 2021*)

Experts have suggested several hormonal drugs, according to steroid receptors identified in leiomyoma tissue. Given the majority of previous and current research that has been carried out in medical treatment for leiomyoma, oral non-hormonal drugs may be on track to overtake other treatment options. Evidence suggests that anti-oxidative mechanisms may lead to a reduction in leiomyoma volume. The administration of NAC as an anti-oxidant reduces oxidative stress by inhibiting free radicals and glutathione synthesis, but its protection is incomplete. As a result, it prevents the peroxidation of membrane lipids and prevents their release (*Tahmasebi et al., 2020*)

The present study is a randomized control trial that aims to assess the impact of NAC versus Dienogest on the volume of uterine leiomyoma.

## 2.AIM / OBJECTIVES

This study aims to assess the effect of Dienogest and NAC on the volume of uterine leiomyoma in women previously diagnosed with leiomyoma.

**Research hypothesis:** In women with leiomyoma, the use of NAC as a non-hormonal drug in the treatment of leiomyoma of the uterus is more feasible and effective in the reduction of leiomyoma volume with no hormonal side effects compared with Dienogest.

**Research question:** In women with leiomyoma, is the use of NAC as a non-hormonal drug in the treatment of leiomyoma of the uterus more feasible and effective in the reduction of leiomyoma volume with no hormonal side effects compared with Dienogest?

### **3.METHODOLOGY:**

#### **Patients and Methods/ Subjects and Methods/ Material and Methods**

##### **Type of Study:**

A Randomized Controlled Trial

##### **Study Setting:**

The study will be conducted at Ain Shams University Maternity Hospital (ASUMH) “outpatient gynaecology clinic”

##### **Study duration:**

After protocol approval till completing of required sample size

##### **Study Population:**

Women attending outpatient gynaecology clinic at Ain Shams University Maternity Hospital with the following criteria:

##### **Inclusion criteria:**

1. Age: 20-45 years.
2. Women with uterine leiomyoma (sub-mucous, sub-serous or intramural) based on transvaginal sonography criteria. Uterine fibroids most often appear as concentric, solid, hypoechoic masses. This appearance results from the prevailing muscle, which is observed at histologic examination. These solid masses absorb sound waves and therefore cause a variable amount of acoustic shadowing.

##### **Exclusion criteria:**

1. Pregnant or menopausal women.
2. History of malignancies, metabolic, hematologic, cardiac, thromboembolism, diabetes, renal or hepatic diseases.
3. History of hormonal drug use or treatment for leiomyoma in the past 3 months.

##### **Sampling Method:**

simple random sample

### **Sample Size:**

The study will be conducted on 40 women; they will be subdivided into 2 equal groups.

Group (A): women will receive Dienogest, with brand name GYNOPROGEST, 2mg pills daily for 3 months (20 cases) (*Ichigo et al., 2011*)

Group (B): women will receive NAC, with brand name GEMACYSTINE, orally at a dose of 600 mg/day for 3 months ( 20 cases) (*Aghaamoo et al., 2021*)

### **Sample size Justification:**

Assuming an effect size of 1.0 reflecting the percentage change (reduction) in the volume of uterine leiomyoma, a sample of 12 patients in each group will be enough to detect such rate, if true, at 0.01  $\alpha$  error and 0.90 power of the test. We will increase the sample to 20 cases in each group to maximize the power of the study.

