**Table 7: Comparison between two groups regarding volume of leiomyoma before and after treatment (largest lesion):**

[figure not shown]
	Group A (Dienogest) (N=20)			Group B (NAC) (N=20)			Z*	P value
	Range	Median	IQR	Range	Median	IQR		
Leiomyoma volume (cm  ) before	1.43-45.24	15.53	4.31-25.01	1.00-108.00	9.00	4.09-14.32	0.52	0.61

Leiomyoma volume (cm  ) after	2.66-76.36	19.54	8.25-32.61	3.24-115.90	13.13	7.74-24.16	0.50	0.63
---	------------	-------	------------	-------------	-------	------------	------	------

\*Mann Whitney U test

Median leiomyoma volume slightly increases after treatment in both groups, but the differences between the groups are not statistically significant ( $p > 0.05$ ), indicating that both treatments had similar effects on leiomyoma volume.

[figure not shown]

[figure not shown]

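### Twelve women per group do not give 90% power at alpha 0.01 for a between-group effect size of 1.0; 32 are needed two-sided (28 one-sided), so 20 is a shortfall and not a surplus

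*Protocol*

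**What the plan says.** The protocol's section on sample size justification opens: "Assuming an effect size of 1.0 reflecting the percentage change (reduction) in the volume of uterine leiomyoma". It states that "a sample of 12 patients in each group will be enough to detect such rate, if true, at 0.01" alpha, with "0.90 power of the test". It continues: "We will increase the sample to 20 cases in each group to maximize the power of the study". It does not name a test, a sidedness, or the mean difference and SD behind the 1.0, and it gives no dropout allowance.

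The rest of the protocol sets a comparison between arms. The hypothesis under Aim / Objectives is that NAC is "more feasible and effective in the reduction of leiomyoma volume with no hormonal side effects compared with Dienogest". The Sample Size section says of the 40 women that "they will be subdivided into 2 equal groups", and randomisation is 1:1.

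SAP Table 7 compares leiomyoma volume between the groups by Mann-Whitney test (P = 0.61 before treatment, 0.63 after). It describes the result as "indicating that both treatments had similar effects on leiomyoma volume".

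**The concern.** An alpha of 0.01 and a power of 0.90 are both demanding, and 12 per group is small for them even when the assumed effect is a full standard deviation. If 12 is too few, the step up to 20 does not add a margin to an adequate design. It may leave the trial below the power it claims.

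This bears on how the result is read. A reader who accepts the justification will take 20 per group to have more than 90% power, and will give weight to a null primary comparison. Table 7 invites that by turning non-significance into a statement of similarity.

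**Working it through.** **Inputs.** Effect size 1.0, alpha 0.01, power 0.90 and 12 per group, raised to 20, all from the sample size justification. Allocation 1:1. *Assumption:* the 1.0 is a standardised between-group mean difference, d = (difference in means)/SD, which fits the hypothesis. Sidedness is not stated, so both are shown.

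**Attempt to reproduce 12, normal approximation.** n per group = 2(z_alpha + z_power)² / d².
- Two-sided: 2 × (2.576 + 1.282)² = 2 × 14.88 = 29.8, so 30.
- One-sided: 2 × (2.326 + 1.282)² = 2 × 13.02 = 26.0, rounded up to 27 (26.03 before rounding).

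Neither gives 12.

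**Exact two-sample t test.** Power comes from the noncentral t distribution with 2n − 2 degrees of freedom and noncentrality d√(n/2). For n = 12 the noncentrality is √6 = 2.45, against critical values of 2.82 two-sided and 2.51 one-sided (22 df). For n = 20 it is √10 = 3.16, against 2.71 and 2.43 (38 df).

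| Quantity (d = 1.0, alpha 0.01) | Two-sided | One-sided |
|---|---|---|
| n per group for 0.90 power | 31.46, so 32 | 27.43, so 28 |
| Required n / stated 12 | 2.7 | 2.3 |
| Power at 12 per group | 0.38 | 0.49 |
| Power at 20 per group | 0.67 | 0.77 |
| d detectable with 0.90 power at 12 | 1.71 | 1.57 |
| d detectable with 0.90 power at 20 | 1.28 | 1.18 |

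The reported Mann-Whitney test does no better here. In simulation (8,000 runs, normal data, 1-SD shift) its power at 20 per group was 0.64 two-sided and 0.74 one-sided. This is illustrative only, because the volumes are skewed.

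**Relaxing alpha.** At 0.05, d = 1.0 still needs 23 per group two-sided or 18 one-sided. Power at 20 is 0.87 two-sided and 0.93 one-sided.

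**Other readings at alpha 0.01.**
- Cohen's f = 1.0 (equal to d = 2.0): 10 per group two-sided or 9 one-sided; two-sided power at 12 is 0.97.
- Paired within-group t test, d = 1.0: 19 two-sided or 16 one-sided. Power at 12 is 0.64 or 0.76; at 20 it is 0.93 or 0.97.
- ANCOVA with 12 per group: reaches 0.90 only if the correlation of baseline with outcome is about 0.81 (0.77 one-sided).

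**What Table 7 can support.** For after-treatment volume Z = 0.50 with 20 per group. Under no difference U has mean 20 × 20 / 2 = 200 and SD √(20 × 20 × 41 / 12) = 36.97. So U = 200 + 0.50 × 36.97 = 218.5, and the probability of superiority is 218.5 / 400 = 0.546. The Hanley-McNeil standard error is 0.092, so the approximate 95% interval is 0.546 ± 1.96 × 0.092, or 0.37 to 0.73 (0.50 means no difference). Ties are ignored, and the sign of Z is not reported, so the direction is unknown.

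**The case against.** The best defence is that the effect size is undefined. The protocol does not call it a standardised between-group difference; it ties it to a percentage change. If it meant Cohen's f, 12 would be more than enough. If it meant a within-group change, 20 would exceed 0.90 power. This is fair, and the finding is conditional for that reason. But no reading tried returns 12 as the required number at the stated alpha and power, a within-group change does not test the hypothesis, and the protocol mentions neither f nor a covariate correlation. The missing definition is itself a defect.

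Second, the shortfall at 20 depends on the 0.01. At one-sided alpha 0.05, 20 per group reaches 0.93. That stands, but 0.01 is the only alpha in the protocol.

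Third, the interval of 0.37 to 0.73 concerns raw after-treatment volume. The baseline medians were 15.53 and 9.00 cm³, and the trial was sized on percentage change. This also stands: the interval shows how little the reported comparison can exclude and does not replace an interval for the difference in change. The objection to inferring similarity from non-significance would hold even if 12 had been correct.

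Fourth, the SAP already reports results for all 40 women, so recruitment cannot change. That affects the form of the remedy and not the error.

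**Conclusion.** The concern holds. On the between-group reading that the hypothesis calls for, the stated inputs require 32 women per group two-sided or 28 one-sided, against 12 claimed. The 20 per group used gives about 67% power two-sided or 77% one-sided at alpha 0.01, so the chance of missing the assumed effect is about 33% or 23%, when the text implies less than 10%. This rests on reading 1.0 as a standardised mean difference and on a t test; it is approximate for the Mann-Whitney test reported.

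The similarity statement under Table 7 is not supported: the after-treatment comparison is compatible with a sizeable difference in either direction, and the SAP gives no equivalence margin or between-group interval.

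A secondary point is that Table 7 judges volume against 0.05 while the protocol's only alpha is 0.01. With P values of 0.61 and 0.63 this changes no between-group volume result, but the documents disagree.

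**What to change.** 1. In the sample size justification, state what the 1.0 is: the test, the sidedness, and the mean difference and SD behind it. If Cohen's f, a paired change or a baseline-adjusted analysis was intended, say so and show the inputs.
2. Otherwise withdraw the claims that 12 per group suffices and that 20 is extra. Replacement text could read: *Twenty women per group give about 67% power at two-sided alpha 0.01 (77% one-sided) for a standardised between-group difference of 1.0 by t test; this is approximate for the Mann-Whitney test reported.* As results are already reported, make this a dated correction.
3. Under SAP Table 7, replace the similarity statement with one that no between-group difference was shown. Add a confidence interval for the between-group difference, preferably in percentage change, since the trial was sized on that.
4. Reconcile the protocol and SAP on the significance level for the primary outcome, without choosing it in the light of the results.

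The cost is one protocol paragraph, one SAP sentence, agreement on the significance level, and one interval from data already held. No patients are added. The downside is a less favourable stated power.

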### **Randomization:**

It will be done using computer generated randomization sheet.

### **Allocation and concealment:**

It will be done by use of sealed opaque packages that will be given to a third person (nurse) who will assign the packages to study groups. Each woman will be invited to pull out a package. According to the number inside her package, women will be allocated to either group A or B according to a computer- generated random list.

### **Blinding:**

The tablets will be enclosed in an opaque packages labelled according to a computer- generated random list. Each woman will be invited to pull out a package. The tablets will be administered anonymously with coding with no knowledge of the codes. Final assessment will be performed by another colleague who will have no information about the groups. Patients and assessor will be blinded to the groups.

### **Ethical and Safety Consideration:**

This study will be done after approval of the Ethical Committee of the Department of Obstetrics and Gynecology, Faculty of Medicine, Ain Shams University. Informed consent will be taken from all participants before recruitment in the study,

and after explaining the purpose and procedures of the study. The investigator will obtain the written, signed informed consent of each subject prior to performing any study specific procedures on the subject. The investigator will retain the original signed informed consent form. All data will be collected confidentially. All cases will be counseled about the side effects associated with study medications. The study will be based on the investigator self-funding.

### **Study procedures and interventions:**

1. After approval of study protocol, women will be enrolled into the study according to inclusion and exclusion criteria.
2. Eligible patients will be randomized using a computer-generated sequence 1:1 either to
3. **Intervention:**
  - Group (A): women will receive Dienogest, with brand name GYNOPROGEST, 2mg pills daily for 3 months (20 cases) (*Ichigo et al., 2011*)
  - Group (B): women will receive NAC, with brand name GEMACYSTINE, orally at a dose of 600 mg/day for 3 months ( 20 cases) (*Aghaamoo et al., 2021*)
4. **Methodology:** All cases will be subjected to:
  - **Full history taking:** with special emphasis to age, parity, BMI, age of menarche, obstetric history, drug history as well as presence of any medical disease.
  - **Full general examination:** for pallor, fatigue.
  - **Abdominal examination:** to assess the leiomyoma size, surface, contour and consistency.
  - **Bimanual vaginal examination(for uterus <12 weeks):** to confirm its uterine origin.
  - **Vaginal Ultrasound examination with the addition of a transabdominal approach if needed** to diagnose and assess the leiomyoma (size and number).

Ultrasound will be done using the same machine.

The principal investigator will hold regular meetings with the research team to assess data and adverse events.

Serious adverse events will be reported to the research ethics committee, Faculty of medicine, Ain Shams university within 24 hours.

### **Outcomes:**

- **Primary outcome:**

**Leiomyoma volume:** Size of myoma will be measured at three diameters of myomas (transverse, vertical and anterior-posterior). These measurements will be repeated after 3 months of therapy by the same sonographer.

- **Secondary outcomes:**

- **Dysmenorrhea:** according to the visual analog scale (VAS) is a validated, subjective measure for acute and chronic pain. The scale is composed of 0 (no pain at all) to 10 (worst imaginable pain).

- **Heavy menstrual bleeding (HMB).**

**1. Actual blood loss per menstrual period:** according to PBAC score is seen in Figure 1, also defined by FIGO System is seen in Figure 2 according to frequency, duration, regularity and flow volume.

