**2. using the measurement of hemoglobin.**

Pads		
1 point	For each lightly stained pad	
5 points	For each moderately stained pad	
20 points	For each completely saturated pad	
Tampons		
1 point	For each lightly stained tampon	
5 points	For each moderately stained tampon	
10 points	For each completely saturated tampon	
Clots/Flooding		
1 point	For each small clot	
5 points	For each large clot	
5 points	For each episode of flooding	

  

Parameter	Normal	Abnormal	
Frequency	Absent (no bleeding) = amenorrhea		
	Infrequent (>38 days)		
	Normal (≥24 to ≤38 days)		
	Frequent (<24 days)		
Duration	Normal (≤8 days)		
	Prolonged (>8 days)		
Regularity	Normal or "Regular" (shortest to longest cycle variation: ≤7-9 days)*		
	Irregular (shortest to longest cycle variation: ≥8-10 days)*		
Flow Volume (patient determined)	Light		
	Normal		
	Heavy		
Intermenstrual Bleeding (IMB) Bleeding between cyclically regular onset of menses	None		
	Random		
	Cyclic (Predictable)	Early Cycle	
		Mid Cycle	
		Late Cycle	
Unscheduled Bleeding on Progestin ± Estrogen  Gonadal Steroids (birth control pills, rings, patches or injections)	Not Applicable (not on gonadal steroid medication)		
	None (on gonadal steroid medication)		
	Present		

**FIGURE 2** The FIGO AUB System (*Munro et al., 2018*)

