**Table 3: Comparison between two groups regarding Gynecological history of patients:**

		Group A (Dienogest) (N=20)		Group B (NAC) (N=20)		$X^2^*$	P value
		N	%	N	%		
Regularity of cycle	Regular	12	60.0%	10	50.0%	0.40	0.53
	Irregular	8	40.0%	10	50.0%		
Contraceptive methods	No	8	40.0%	7	35.0%	2.15	0.67

	IUD	10	50.0%	10	50.0%	FE	
	OCP	2	10.0%	1	5.0%		
	Tubal ligation	0	0.0%	2	10.0%		
Previous complications from contraceptive method	No	20	100.0%	20	100.0%	-	-

\*Chi square test (FE: Fisher Exact)

Both groups show a similar distribution in terms of cycle regularity and contraceptive methods.

The use of contraceptive methods like IUDs is equally common in both groups (50%), suggesting similar baseline characteristics for contraceptive use.

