**Table 9: Comparison between two groups regarding HMB assessment before and after treatment:**

	Group A (Dienogest) (N=20)			Group B (NAC) (N=20)			Z*	P value
	Range	Median	IQR	Range	Median	IQR		
HMB assessment (PBAC) before	10.00-200.00	70.00	15.00-110.00	10.00-200.00	50.00	15.00-90.00	0.9	0.86
HMB assessment (PBAC) after	.00-200.00	.00	.00-9.00	3.00-200.00	25.00	15.00-70.00	4.10	0.00

\*Mann Whitney U test

Group A shows a significant reduction in PBAC scores after treatment, indicating a better response to treatment compared to Group B (P value = 0.00).

[figure not shown]

[figure not shown]

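### PBAC is scored per menstrual period, a unit that a daily progestin can remove or change, so the zero scores behind the dienogest result in SAP Table 9 have no defined meaning

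*Protocol*

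**What the plan says.** Protocol, Outcomes, lists heavy menstrual bleeding as a secondary outcome. Its first measure is "Actual blood loss per menstrual period" by PBAC, and it is "also defined by FIGO System is seen in Figure 2 according to frequency, duration, regularity and flow volume". Hemoglobin is the second measure.

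The FIGO form in Figure 2 has a line "Absent (no bleeding) = amenorrhea", a block for intermenstrual bleeding, and a block headed "Unscheduled Bleeding on Progestin ± Estrogen". No rule links any of these to the PBAC score.

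No window or time point is given for PBAC. The only timing statement under Outcomes belongs to the myoma diameters: "These measurements will be repeated after 3 months of therapy by the same sonographer". Study procedures and interventions gives group A dienogest daily for 3 months and describes no bleeding chart.

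The SAP compares one PBAC value per woman by Mann-Whitney test (Table 9) and concludes: "Group A shows a significant reduction in PBAC scores after treatment, indicating a better response to treatment compared to Group B". It reports no FIGO item after treatment. Table 3 gives cycle regularity as baseline history.

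**The concern.** An outcome unit should mean the same thing in both arms and should not itself be altered by treatment. A menstrual period fails that test when one arm takes a daily progestin. For a woman with no period the score is undefined. For a woman who bleeds outside a period, a literal reading leaves that bleeding out. A score of 0 could then mean that she did not bleed, or that she bled but had no period to score.

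The distinction matters because PBAC is one of only two outcomes with a significant difference between arms after treatment. The other is dysmenorrhea VAS (Table 8, P = 0.001). Table 9 is also the basis for the SAP's statement that dienogest gave the better response on bleeding.

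**Working it through.** **Inputs.** SAP Table 9, after treatment: dienogest n = 20, range 0-200, median 0, IQR 0-9; NAC n = 20, range 3-200, median 25, IQR 15-70; Z = 4.10, P = 0.00. SAP Table 3: irregular cycles in 8/20 and 10/20, chi-square 0.40, P = 0.53. SAP Tables 10 to 12: hemoglobin. Protocol PBAC points: a moderately stained pad scores 5.

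**1. Printed figures.**
- Z = 4.10 gives two-sided P = 0.00004, consistent with the printed 0.00.
- Pearson chi-square on 12/8 against 10/10 is 0.404, P = 0.525, as printed.
- The baseline PBAC row does not agree with itself: Z = 0.9 gives P = 0.37, not the printed 0.86. That does not affect this point.

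**2. How many zeros.** With n = 20 the median is the mean of the 10th and 11th ordered values. Scores cannot be negative, so a median of 0 makes both of them 0. At least 11 of 20 dienogest women therefore scored 0. The NAC minimum of 3 means that no NAC woman did.

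**3. What a literal reading can leave out.** Assume 10 days of unscheduled bleeding with two moderately stained pads a day: 10 × 2 × 5 = 100 points. The dienogest baseline median is 70. The same bleeding scores 0 if only menstrual periods count. The days and pads are assumptions, not trial data.

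**4. Sensitivity on assumed data.** Individual scores are not published, so these sets only approximate the printed summaries.
- NAC: 3, 5, 8, 12, 15, 15, 15, 20, 20, 25, 25, 30, 40, 55, 70, 70, 80, 100, 150, 200.
- Dienogest: from 11 zeros plus 3, 5, 6, 8, 9, 15, 30, 60, 200, up to 14 zeros plus 8, 9, 15, 30, 60, 200.
- Unchanged, these give Z of 3.8 to 4.0 and P of about 0.0001.

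| Change to the assumed data | P |
|---|---|
| Scores rescaled to 90 days, random cycle lengths of 24-38, 15-60 or 15-90 days | at most 0.0024 |
| Zero-score women left out as having no period (6 to 9 dienogest women remain) | 0.16 to 0.83 |
| 7 zero-score women given scores drawn from the NAC set | median 0.04 to 0.06 |
| 8 zero-score women given scores drawn from the NAC set | median 0.07 to 0.11 |

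The second row is not a proposed analysis, because it selects women on a result of treatment. It shows only how much rests on the meaning of 0.

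**5. Irregular cycles.** 8 + 10 = 18 of 40 (45%), balanced between arms and slightly more frequent on NAC. At an assumed 50 points per period, a 21-day cycle gives 50 × 30/21 = 71 points per 30 days and a 45-day cycle gives 50 × 30/45 = 33. That is noise within both arms and has no direction.

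**6. Hemoglobin.**
- Change: 10.99 − 10.54 = 0.45 (dienogest) and 11.63 − 11.39 = 0.24 (NAC). Difference: 0.21.
- Standard errors from the printed paired t values: 0.45/2.78 = 0.162 and 0.24/1.40 = 0.171.
- Standard error of the difference: √(0.162² + 0.171²) = 0.24.
- The difference is smaller than its standard error, so it is inconclusive.

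**The case against.** The strongest reply is that a woman who does not bleed scores 0 over any window. True amenorrhea on dienogest would explain Table 9 with no artefact, and no rescaling for time changes a zero. No document reports unscheduled bleeding in any dienogest woman. The FIGO form is a published generic instrument, and it gives the protocol a place to record such bleeding. All of this stands. It does not close the gap, because no rule carries the form's entries into the score and the SAP reports none of them after treatment.

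A reader might infer that the comparison used unequal observation times and so favours dienogest. The documents do not support that. No observed time is given for either arm. Unscored unscheduled bleeding would favour dienogest, but a long irregular bleed charted as one period would work against it. The irregular cycles do not supply a direction either: the SAP notes that "Both groups show a similar distribution in terms of cycle regularity and contraceptive methods".

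A reader might also take hemoglobin as contradicting PBAC, since the after-treatment P is 0.17. That test compares levels, and NAC started 11.39 − 10.54 = 0.85 higher. The gap narrowed to 11.63 − 10.99 = 0.64, and the within-arm rise was significant only on dienogest (P = 0.01 against 0.18). Hemoglobin neither confirms nor contradicts the PBAC result.

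The missing charting step in the procedures section proves little by itself. That section describes no VAS or hemoglobin assessment either, yet the SAP has baseline values for both.

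**Conclusion.** The concern holds as a defect of definition. The PBAC unit can be changed by one of the two treatments, and the protocol does not say what a woman without a period scores or whether bleeding outside a period counts. At least 11 of 20 dienogest scores, and no NAC score, are zeros whose meaning the documents leave open. That count rests only on the printed median, the group size and non-negative scores.

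The possible effect on P is known only from assumed data. The difference survives rescaling for cycle length. It would lose significance only if roughly 7 or 8 zero-score women had uncounted bleeding at NAC levels. Neither the occurrence of such bleeding nor a net direction of bias is shown. This is a secondary outcome, so the point is a worthwhile correction and not a threat to the trial's primary comparison.

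**What to change.** In the protocol's Outcomes section, define the measure as the total PBAC score over a fixed calendar window of the same stated length in both arms, once before the first dose and once at the end of treatment. Count all bleeding, menstrual or not, and score 0 only when there was no bleeding in the window. Thirty days is one possible length. A longer window is less likely to miss a period in a woman in the form's infrequent category (cycles over 38 days).

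Beside Table 9, report the post-treatment FIGO items: amenorrhea, intermenstrual bleeding and unscheduled bleeding.

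The SAP already holds results, so first state which window was used and how women without a period were scored. Table 9 can be recalculated on the new definition only if daily charts exist. If only per-period scores exist, limit its conclusion to *lower menstrual-period PBAC score* and drop the claim of a better response.

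The cost is somewhat longer charting and possibly a short wait before the first dose if the baseline window is charted prospectively. Narrowing the conclusion needs no new data.
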